5.0 Analysis Populations

5.1 Definition for Analysis Populations

The following populations will be used for analyses in the study:

Modified Intent-to-Treat (mITT) set includes all ITT subjects who achieve clinical response (CR-70) at Week 12. The mITT set is the primary population for the efficacy analysis for the Maintenance Study.

The safety set consists of all subjects who received at least one injection of study drug during maintenance study. The safety set will be analyzed as treated, according to treatment the subject actually received. The safety set will be used only for safety analysis.

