For safety related analyses, if multiple measurements are made for a particular laboratory or vital sign parameter on the same day for the same subjects, the one with later time will be used if collection time is also available, or the average of the values will be used in the analyses of change from Baseline. For summaries and listings for shift from baseline and potentially significant values, all collected values within the pre-specified treatment window will be used.

Definition of Analysis Windows

Since subjects do not always adhere to the study visit schedule, the following rules will be applied to assign actual visits to protocol-specified visits including early termination visits. For each study visit mentioned in the protocol, a nominal or target day will be selected to represent the corresponding visit along with a window around the target day. Windows will be selected in a non-overlapping fashion so that a date collected on the CRF does not correspond to multiple visit windows. Moreover, windows will not discard any Post-Baseline measurement recorded on the CRF. If a subject had two or more actual visits in one visit window, the visit closest to the schedule visit will be used as the study visit for that window. If two visits are equidistant from the target, then the later visit will be used for reporting. If more than one assessment is collected on the same day, then the average of those assessments will be used in analyses.

Table 3. Visit Windows for Analysis of CDAI and Vital Signs for Maintenance Study

Scheduled Week	Nominal Day	Time Window (Rx Day Range)
Week 12 (Week 0 of Maintenance Study)	1 ^a	≤ 1
Week 14 (Week 2 of Maintenance Study)	15	2 – 36
Week 20 (Week 8 of Maintenance Study)	57	37 – 78
Week 26 (Week 14 of Maintenance Study)	99	79 – 106
Week 28 (Week 16 of Maintenance Study)	113	107 – 134
Week 34 (Week 22 of Maintenance Study)	155	135 – 176
Week 40 (Week 28 of Maintenance Study)	197	177 – 204
Week 42 (Week 30 of Maintenance Study)	211	205 – 232
Week 48 (Week 36 of Maintenance Study)	253	233 – 281
Week 56 (Week 44 of Maintenance Study)	309	282 – 379

Rx Day = date of visit – date of first study drug injection in double-blind maintenance study + 1

- a. Day of first dose of study drug in double-blind maintenance study. If a subject has not taken any study drug during Maintenance Study, the randomization date will be use as Day 1 of Maintenance Study.

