For safety related analyses, if multiple measurements are made for a particular laboratory or vital sign parameter on the same day for the same subjects, the later time one will be used if there is time or the average of the values will be used in the analyses of change from Baseline. For summaries and listings for shift from baseline and potentially significant values, all collected values within the pre-specified treatment window will be used.

Definition of Analysis Windows

Since subjects do not always adhere to the study visit schedule, the following rules will be applied to assign actual visits to protocol-specified visits including early termination visits. For each study visit mentioned in the protocol, a nominal or target day will be selected to represent the corresponding visit along with a window around the target day. Windows will be selected in a non-overlapping fashion so that a date collected on the CRF does not correspond to multiple visit windows. Moreover, windows will not discard any Post-Baseline measurement recorded on the CRF. If a subject had two or more actual visits in one visit window, the visit closest to the schedule visit will be used as the study visit for that window. If two visits are equidistant from the target, then the later visit will be used for reporting. If more than one assessment is collected on the same day, then the average of those assessments will be used in analyses.

Table 2. Visit Windows for Analysis of Efficacy Variables (Except IBDQ, EQ-5D, WPAI, and SES CD), hs-CRP, Urinalysis and Vital Signs for Induction Study

Scheduled Week	Nominal Day	Time Window (Rx Day Range)
Week 0	1 ^a	≤ 1
Week 2	15	2 – 22
Week 4	29	23 – 36
Week 6	43	37 – 50
Week 8	57	51 – 71
Week 12	85	72 – 98 ^b

Rx Day = date of visit – date of first study drug injection in double-blind induction study + 1

- a. Day of first dose of study drug in double-blind induction study. If a subject has not taken any study drug during Induction Study, the randomization date will be use as Day 1.
- b. Rx Day 98, or first dose of maintenance, or first dose of study drug in Study M14-347, whichever earlier.

Table 3. Visit Windows for Analysis of IBDQ, EQ-5D, and WPAI

Scheduled Week	Nominal Day	Time Window (Rx Day Range)
Week 0	1 ^a	≤ 1
Week 4	29	2 – 43
Week 8	57	44 – 71
Week 12	85	72 – 98 ^b

Rx Day = date of visit – date of first study drug injection in double-blind induction study + 1

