- a. Day of first dose of study drug in double-blind induction study. If a subject has not taken any study drug during Induction Study, the randomization date will be use as Day 1.
- b. Rx Day 98, or first dose of maintenance, or first dose of study drug in Study M14-347, whichever earlier.

Table 4. Visit Windows for Analysis of Chemistry and Hematology for Induction Study

Scheduled Week	Nominal Day	Time Window (Rx Day Range)
Week 0	1 ^a	≤ 1
Week 2	15	2 - 22
Week 4	29	23 – 43
Week 8	57	44 – 71
Week 12	85	72 – 98 ^b

Rx Day = date of visit – date of first study drug injection in double-blind induction study + 1

- a. Day of first dose of study drug in double-blind induction study. If a subject has not taken any study drug during Induction Study, the randomization date will be use as Day 1.
- b. Rx Day 98, or first dose of maintenance, or first dose of study drug in Study M14-347, whichever earlier.

Table 5. Visit Windows for Analysis of SES-CD, Fistulas, and EIM for Induction Study

Scheduled Week	Nominal Day	Time Window (Rx Day Range)
Week 0	1 ^a	≤ 1
Week 12	85	2 – 168 ^b

Rx Day = date of visit – date of first study drug injection in double-blind induction study + 1

- a. Day of first dose of study drug in double-blind induction study. If a subject has not taken any study drug during Induction Study, the randomization date will be use as Day 1.
- b. Rx Day 168, or first dose of maintenance + 7 days, or first dose of study drug in Study M14-347 + 7 days, whichever earlier. No + 7 days for Fistulas and EIM.

Table 6. Visit Windows for Analysis of Fecal Calprotectin for Induction Study

Scheduled Week	Nominal Day	Time Window (Rx Day Range)
Week 0	1 ^a	≤ 1
Week 4	29	2 – 57
Week 12	85	58 – 112 ^b

Rx Day = date of visit – date of first study drug injection in double-blind induction study + 1

- a. Day of first dose of study drug in double-blind induction study. If a subject has not taken any study drug during Induction Study, the randomization date will be use as Day 1.
- b. Rx Day 112, or first dose of maintenance, or first dose of study drug in Study M14-347, whichever earlier.

CD-Related Concomitant Corticosteroid Therapy

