12.0 Summary of Changes

12.1 Summary of Changes Between the Latest Version of Protocol and the Current SAP

None.

12.2 Summary of Changes Between the Previous Version and the Current Version of the SAP

Under Section 6.0 Analysis Conventions: Only CD related systemic or rectal corticosteroids will be used for censoring purpose, and will have last non-missing value prior to censoring carried forward for non-categorical assessments) from that point forward. This change is made to be consistent with protocol Amendment 6.

In addition, SES-CD scoring rule is updated regarding missing individual variables. The missing SES-CD individual variables at Baseline will be imputed as 0. The post-Baseline missing SES-CD individual variables will be imputed as 0 if there are 8 or fewer missing individual variables. If more than 8 individual variables are missing, the total SES-CD will be missing for that visit. Both changes are based on newly created Analysis Convention for Crohn's Disease and Ulcerative Colitis Clinical Studies. The new imputation rule is also used by current Abbvie IBD registrational trials.

Bristol Stool Form Scale is not a continuous variable. The new variable Bristol Stool Chart score is defined as the number of days the subjects with Type 6 or Type 7 divided by the total number days with non-missing assessments, rounded to two decimal. If a subject achieved reduction from Baseline $\geq 50\%$, this subject will be classified as Bristol Stool Chart Responder. This change is made to be consistent with protocol Amendment 6.

The Week 12 visit window for SES-CD is updated so that no post-baseline Induction data will be discarded. In addition, endoscopy data collected prior to or within 7 days of the fist dose of maintenance study or OLE Study M14-347 will be considered for the Week 12 visit window for SES-CD; thus ensuring endoscopy data collected is not ignored

while also reflecting the efficacy based on the study treatment during the 12 week induction period.

Under Section 10.2, one of the co-primary endpoints, SES-CD ≤ 4 and at least a 2 point reduction versus baseline and no subscore greater than 1 in any individual variable) at Week 12 is replaced by decrease in SES-CD $> 50\%$ from Baseline (or for a Baseline SES-CD of 4, at least a 2 point reduction from Baseline) at Week 12. This change is made to be consistent with protocol Amendment 6.

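### Induction SAP Tables 2 and 3 close Week 12 at Day 98, against the SAP's own rule that no recorded post-Baseline value is discarded; seven ranked secondary endpoints are exposed

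*SAP*

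**What the plan says.** Four statements in the Induction SAP bear on this.

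- Section 6.0, Definition of Analysis Windows, sets the general rule: "Moreover, windows will not discard any Post-Baseline measurement recorded on the CRF".
- Section 6.0, Definition of Induction Final Observation, places efficacy, laboratory and vital sign evaluations made on the day of the first maintenance (or Study M14-347) dose in the Induction analyses. It attaches no day limit.
- Table 2, "Visit Windows for Analysis of Efficacy Variables (Except IBDQ, EQ-5D, WPAI, and SES CD), hs-CRP, Urinalysis and Vital Signs for Induction Study", and Table 3, "Visit Windows for Analysis of IBDQ, EQ-5D, and WPAI", give Week 12 a range of Day 72 to 98. Footnote b closes it at "Rx Day 98, or first dose of maintenance, or first dose of study drug in Study M14-347, whichever earlier". Table 4 (chemistry and hematology) has the same cap.
- Table 5 closes the SES-CD window at "Rx Day 168, or first dose of maintenance + 7 days, or first dose of study drug in Study M14-347 + 7 days, whichever earlier". Table 6 closes fecal calprotectin at Day 112 or the first maintenance or M14-347 dose. Section 12.2 explains the SES-CD change: "The Week 12 visit window for SES-CD is updated so that no post-baseline Induction data will be discarded".

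In the Maintenance SAP, the row "Week 12 (Week 0 of Maintenance Study)" of Tables 3 and 4 takes any value with maintenance Rx Day of 1 or less. Section 5.1 of that SAP says the mITT set "includes all ITT subjects who achieve clinical response (CR-70) at Week 12", without saying which window supplies that CDAI.

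**The concern.** Week 12 is the last Induction window. A CDAI, hs-CRP or IBDQ value recorded on Day 99 or later, but on or before the first maintenance dose, therefore belongs to no Induction visit. The general rule says such a value is kept. The Final Observation text says it is used if it falls on the dosing day. The tables say neither.

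The choice affects results. Under non-responder imputation, a missing binary endpoint counts as a failure, so a subject measured in remission on Day 100 would be analysed as not in remission. The ranked endpoints are tested in fixed order and testing stops at the first failure; ranks 1 and 3 are among those exposed. If the texts are not reconciled beforehand, the decision is left to programming.

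**Working it through.** **Reproducing the windows.** Nominal Week 12 is 12 × 7 + 1 = Day 85. The three table ranges are symmetric about it:

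- CDAI, hs-CRP, IBDQ (Tables 2 and 3): 85 ± 13 = 72 to 98
- Fecal calprotectin (Table 6): 85 ± 27 = 58 to 112
- SES-CD (Table 5): 85 ± 83 = 2 to 168

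**Mapping one visit.** Suppose all Week 12 assessments and the first maintenance dose fall on the same day.

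| Rx Day | CDAI, hs-CRP, IBDQ | Calprotectin | SES-CD | Maintenance SAP, Tables 3 and 4 |
|---|---|---|---|---|
| 98 | Week 12 | Week 12 | Week 12 | Week 12 |
| 99 | no window | Week 12 | Week 12 | Week 12 |
| 112 | no window | Week 12 | Week 12 | Week 12 |

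**What then happens to the value.** This assumes that no other value falls in Days 72–98.

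- Binary endpoints: not achieved, under NRI (sections 6.0 and 10.3).
- Continuous endpoints: LOCF, the primary method, carries forward an earlier post-Baseline visit.
- Observed-case analysis: Week 12 stays missing.

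**Endpoints exposed (section 10.3).** Week 12 CDAI enters ranked endpoints 1, 3, 4, 9 and 12; Week 12 IBDQ enters 14 and 15. That is 5 + 2 = 7 of 15. Week 12 hs-CRP enters only endpoint 9, which combines components capped at Day 98 (CDAI, hs-CRP), 112 (calprotectin) and 168 (SES-CD). The co-primaries use Week 4 CDAI and Week 12 SES-CD, and ranked endpoint 2 uses the same two measures, so none of the three is touched. The stated power concerns the co-primaries only. Exact Fisher calculations with 300 versus 200 give 99.4% (50% vs 30%) and 99.8% (66% vs 44%), in line with the plan.

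**How late is Day 99?** The protocol's visit tolerance of ± 3 days (Table 3, note a) allows Day 82 to 88. Day 99 is 99 − 85 = 14 days after nominal and 99 − 88 = 11 days beyond tolerance.

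**Size, under assumptions.** The documents give no count of late visits. Let f be the share of subjects with only a late value, equal in both arms, with late subjects remitting as often as the others. Each observed rate, and the difference, is multiplied by (1 − f).

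- At f = 1–5% (5–25 of 500) and 50% remission: loss = f × 50% = 0.5–2.5 points.
- Power illustration, normal approximation, 300 vs 200: 47% in the standard arm (Week 12 remission on 160/80 in Study M05-769, protocol Table 1) against an assumed 60%.

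| f | Difference (points) | Power |
|---|---|---|
| 0 | 13.00 | 81.7% |
| 1% | 12.87 | 80.9% |
| 2% | 12.74 | 80.1% |
| 5% | 12.35 | 77.4% |

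**Would a wider window disturb anyone else?** No. When two visits share a window, the closer one is used. A value in Days 72–98 is at most 13 days from Day 85; one from Day 99 on is at least 14 days away and can never displace it.

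**The case against.** The strongest reply is that window width is a design choice. CDAI is measured at five post-Baseline Induction visits and endoscopy at one, so a wider SES-CD window is reasonable, and section 12.2 justifies the change for SES-CD only. A CDAI taken two weeks late may be a poor Week 12 value. That argument would support a stated cap. It does not reconcile a cap with an unqualified rule that nothing is discarded, nor with the Final Observation text.

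Four stronger readings are tempting but not supported.

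- **Bias between arms.** A reader might infer that dosing interruptions, for instance for infection, delay Week 12 more often in one arm. Protocol 6.1.7 interrupts injections and does not mention visits. Visits and dosing dates are anchored to Baseline (protocol Table 3 note a, 5.3.1.1 and 5.5.4). Nothing shows that interruption moves the Week 12 visit, or does so unequally. A late endoscopy need not delay it either, since Table 5 accepts endoscopies up to 7 days after the first maintenance dose.
- **A responder in one SAP and a non-responder in the other.** This is possible, because Maintenance Table 3 would accept the late CDAI. But the Maintenance SAP does not say that its own window defines CR-70 for the mITT set, and its endpoints are exploratory and non-ranked.
- **Every late value becomes a failure.** That holds for binary endpoints only; changes in hs-CRP, IBDQ, EQ-5D and WPAI are handled by LOCF.
- **No analysis uses the late value.** The Final Observation text would include one taken on the dosing day, and the time-to-remission and time-to-response endpoints are date-based and not expressly tied to Table 2.

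**Conclusion.** The inconsistency is real and lies within section 6.0 of the Induction SAP. Applied literally, the tables leave a recorded, pre-maintenance CDAI, hs-CRP or IBDQ value from Day 99 onward without a visit, against two other statements in the same section. Seven ranked secondary endpoints are exposed.

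The effect is probably small, since only visits at least 11 days outside tolerance are caught, and only where nothing else falls in Days 72–98. The 0.5–2.5 points and the fall in power from 81.7% to between 80.9% and 77.4% rest on an assumed late share of 1–5%, the same in both arms, and on assumed remission rates. The documents do not show a difference between arms, nor that the fixed testing sequence would in fact be broken. The point should be settled because the remedy is cheap and the SAP has already made a similar change for SES-CD for this stated reason.

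**What to change.** - **Tables 2 and 3, and Table 4 for laboratory data:** for subjects who continue, end Week 12 at the first maintenance or M14-347 dose, that day included, with an outer bound such as the Day 168 already used for SES-CD. Without an outer bound, a very late value could pass as Week 12.
- **Subjects who enter neither study:** keep Day 98.
- **No-discard sentence:** qualify it to name the caps that remain, including Day 112 for calprotectin in Table 6.
- **Maintenance SAP 5.1:** state that the same Week 12 CDAI defines CR-70 for the mITT set.

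If the sponsor prefers to keep Day 98 for everyone, it should state the cap as a deliberate exception to both the no-discard sentence and the Final Observation text, and add a sensitivity analysis using the late values.

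The cost is a footnote and two sentences. The downside is that a few Week 12 values would come from visits two or more weeks late, though still before or on the day of the first maintenance dose.

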Table 4. Visit Windows for Analysis of Chemistry, Hematology, Urinalysis, hs-CRP, Fecal Calprotectin, Abdominal Pain Rating Scale, IBDQ, EQ-5D, and WPAI for Maintenance Study

Scheduled Week	Nominal Day	Time Window (Rx Day Range)
Week 12 (Week 0 of Maintenance Study)	1 ^a	≤ 1
Week 26 (Week 14 of Maintenance Study)	99	2 – 148
Week 40 (Week 28 of Maintenance Study)	197	149 – 253
Week 56 (Week 44 of Maintenance Study)	309	254 – 379

Rx Day = date of visit – date of first study drug injection in double-blind maintenance study + 1

- a. Day of first dose of study drug in double-blind maintenance study. If a subject has not taken any study drug during Maintenance Study, the randomization date will be use as Day 1 of Maintenance Study.

Table 5. Visit Windows for Analysis of SES-CD for Maintenance Study

Scheduled Week	Nominal Day	Time Window (Rx Day Range)
Week 12 (Week 0 of Maintenance Study)	1 ^a	≤ 1
Week 56 (Week 44 of Maintenance Study)	309	2 – 379

Rx Day = date of visit – date of first study drug injection in double-blind maintenance study + 1

- a. Day of first dose of study drug in double-blind maintenance study. If a subject has not taken any study drug during Maintenance Study, the randomization date will be use as Day 1 of Maintenance Study.

Table 6. Visit Windows for Analysis of Fistulas and EIM for Maintenance Study

Scheduled Week	Nominal Day	Time Window (Rx Day Range)
Week 12 (Week 0 of Maintenance Study)	1 ^a	≤ 1
Week 56 (Week 44 of Maintenance Study)	309	2 – 379

Rx Day = date of visit – date of first study drug injection in double-blind maintenance study + 1

- a. Day of first dose of study drug in double-blind maintenance study. If a subject has not taken any study drug during Maintenance Study, the randomization date will be use as Day 1 of Maintenance Study.

CD-Related Concomitant Corticosteroid Therapy

Subjects in whom the CD-related corticosteroids (systemic or rectal corticosteroids) that were not being taken at Induction Baseline and are initiated during the study or who have equivalent dose of these medications increased to greater than the dose taken at Induction Baseline will be censored for efficacy assessments (i.e., will be considered non-responders for categorical endpoints and will have last non-missing values carried forward for non-categorical assessments) from that point through the end of the study. These subjects will continue to be evaluated in the safety population.

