Subjects in whom systemic corticosteroids were used at Induction Baseline and initiated rectal corticosteroids during the study will be censored for efficacy assessment, regardless of rectal corticosteroid dose.

The equivalent steroid dose will be determined based on the table below:

Corticosteroid	Equivalent Dose (mg)
Cortisone	25
Hydrocortisone	20
Prednisone	5
Prednisolone	5
Triamcinolone	4.0
Methylprednisolone	4.0
Betamethasone	0.75
Dexamethasone	0.75
Budesonide	1
Beclomethasone	5
Beclometasone	5

Definition of Missing Data Imputation

The following imputation methods will be used to impute missing values in the efficacy analyses. In addition, an observed case analysis will be performed.

Non-Responder Imputation (NRI)

The NRI approach is used for binary efficacy variables. These variables can take values of 'Achieved' or 'Not Achieved' or may be missing for any reason including discontinuation from study. According to the NRI imputation approach, all missing values will be considered as 'Not Achieved.'

Last Observation Carried Forward (LOCF)

For all variables (categorical variables and continuous variables), the following rules will be used for the LOCF approach:

1. Maintenance Baseline and Pre-Maintenance Baseline values will not be used to impute the missing Post-Maintenance Baseline values.

2. Missing values after Study Day 1 will be imputed using the latest non-missing values after Day 1 and prior to the missing value. If there are no non-missing values after Maintenance Baseline, then the LOCF value will be missing.

Mixed-Effect Model Repeated Measure (MMRM)

The MMRM model will be used for continuous efficacy variables with longitudinal data as a sensitivity analysis. The MMRM model includes the Induction baseline values as covariate; randomization strata, region (US versus non-US), treatment, time point and treatment-by-time point interaction as fixed effects; and subjects within treatment as random effect. An unstructured (co)variance structure will be used to model the within-subject error. The comparison at a time point will be the contrast between treatments at that time point.

Observed Case (OC)

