10.2 Efficacy Analyses

This section provides the details of the efficacy analysis for the Maintenance Study.

For these endpoints which are categorical variables, NRI method of imputation will be used for the missing values. LOCF will be used as a sensitivity analysis wherever applicable.

Both LOCF and OC analyses will be performed for continuous endpoints. The LOCF analysis is considered primary for inferential purposes. In addition, Mixed-Effect Model Repeated Measure (MMRM) will be applied as a sensitivity analysis, wherever appropriate, for the longitudinal continuous endpoints.

For endoscopy related endpoints, there will be no LOCF imputation as there is only one post-baseline endoscopy during Maintenance. OC will be used as a sensitivity analysis.

The difference in proportions of subjects between treatment groups will be analyzed using the two-sided Cochran-Mantel-Haenszel (CMH) test adjusted for induction treatment regimen, and decrease in SES-CD > 50% from Induction Baseline per central reading at Week 12. Additionally, the CMH-based two-sided 95% confidence interval (CI) for the difference in the proportions between the treatment groups will be calculated.

The difference in change from Induction Baseline between treatment groups will be analyzed using an ANCOVA model including factors of treatment, induction treatment regimen, decrease in SES-CD > 50% from Induction Baseline per central reading at Week 12 and Induction Baseline values. Parameter estimates with 95% confidence interval and *P*-value will be provided.

All efficacy endpoints for Maintenance Study are non-ranked.

- Proportion of subjects who achieve endoscopic response (SES-CD > 50% from Induction Baseline [or for a Induction Baseline SES-CD of 4, at least a 2 point

reduction from Induction Baseline]) at Week 56 among subjects with endoscopic response at Week 12

- Proportion of subjects who achieve endoscopic remission ($\text{SES-CD} \leq 4$ and at least a 2 point reduction versus Induction Baseline and no subscore greater than 1 in any individual variable) at Week 56 among subjects with endoscopic remission at Week 12.
- Proportion of subjects who achieve endoscopic remission ($\text{SES-CD} \leq 4$ and at least a 2 point reduction versus Induction Baseline and no subscore greater than 1 in any individual variable) at Week 56 among subjects with endoscopic response at Week 12.

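### The two SAPs assign an SES-CD scan taken 1 to 7 days after the first maintenance dose to different visits: Week 12 in the induction analysis, the Week 56 window in the maintenance analysis

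*SAP*

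**What the plan says.** **Induction SAP.** Section 6.0, Table 5, footnote b, ends the Week 12 SES-CD window at "Rx Day 168, or first dose of maintenance + 7 days" (or the same margin after the first dose in the extension study), whichever comes first. Fistulas and extra-intestinal manifestations do not get the extra 7 days. Section 12.2 shows that the rule is deliberate: it admits "endoscopy data collected prior to or within 7 days of the fist dose of maintenance study" to Week 12 so that no scan is lost, "while also reflecting the efficacy based on the study treatment during the 12 week induction period".

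**Maintenance SAP.** The SES-CD table in section 6.0 ("Table 5. Visit Windows for Analysis of SES-CD for Maintenance Study") sets Week 12 at Rx Day 1 or earlier and Week 56 at Rx Days 2 to 379, with nominal Day 309. There is no 7-day allowance. The same section dates the Maintenance Baseline value no later than Day 1. On competing scans it says: "If a subject had two or more actual visits in one visit window, the visit closest to the schedule visit will be used".

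**Where Week 12 status is used.** In Maintenance SAP section 10.2 the CMH and ANCOVA analyses adjust for "decrease in SES-CD > 50% from Induction Baseline per central reading at Week 12". Three endpoints have a denominator defined by Week 12 endoscopic status:
- response among Week 12 responders;
- remission among Week 12 remitters;
- remission among Week 12 responders, worded "at Week 56 among subjects with endoscopic response at Week 12".

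Section 10.2 does not say which SAP's window supplies the Week 12 value. Section 12.1 of the Maintenance SAP does not mention the difference.

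**The concern.** Each table is free of overlap on its own. Across the two plans, though, one scan date can belong to two visits. The Induction SAP gives a reason for treating such a scan as an induction result, and the Maintenance SAP then places it in the window for the end-of-maintenance result.

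Two things are at stake. First, a subject can be a Week 12 endoscopic responder in the induction report and have no Week 12 status in the maintenance report. Second, a subject with no later scan can be credited with a Week 56 endoscopic outcome from a scan taken within a week of starting maintenance. Under the Induction SAP's assignment that subject has no Week 56 scan, and non-responder imputation would apply.

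**Working it through.** **Inputs.**
- Both SAPs, notes under the window tables: Rx Day = visit date − date of first dose in that part of the study + 1.
- Induction SAP, Table 5: nominal Week 12 is Day 85 (12 × 7 + 1). With the first maintenance dose on induction Rx Day D, the window ends at min(168, D + 7).
- Maintenance SAP, Table 5: Week 12 is Rx Day ≤ 1; Week 56 is Rx Days 2 to 379; nominal Week 56 is Day 309 ((56 − 12) × 7 + 1).

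**Step 1: put both limits on one scale.** The first maintenance dose is maintenance Rx Day 1, so 7 days later is Rx Day 8. At D = 85 the induction window ends on Day 92, and 92 − 85 + 1 = 8.

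**Step 2: compare assignments (D = 85).**

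| Scan relative to first maintenance dose | Maintenance Rx Day | Induction SAP | Maintenance SAP |
|---|---|---|---|
| same day | 1 | Week 12 | Week 12 |
| 1 to 7 days after | 2 to 8 | Week 12 | Week 56 window |
| 8 days after | 9 | outside | Week 56 window |

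Days in conflict: 8 − 2 + 1 = 7.

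**Step 3: effect of the Day 168 cap.** The cap applies only if D + 7 > 168, that is D ≥ 162, which is 162 − 85 = 77 days later than nominal. For D ≤ 161 all 7 days conflict. At D = 164 the induction window ends on Rx Day 168 − 164 + 1 = 5, so the conflict covers Rx Days 2 to 5. At D = 168 there is none.

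**Step 4: when the early scan becomes the Week 56 value.** A scan on Rx Days 2 to 8 lies 309 − 8 = 301 to 309 − 2 = 307 days from nominal. Any scan on Rx Days 9 to 379 lies at most 300 days away (309 − 9 = 300; 379 − 309 = 70). The closest-visit rule therefore always prefers a later scan, and the early one is used only if it stands alone.

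**Step 5: consequences for a subject whose only Week 12 scan is on Rx Days 2 to 8, with Maintenance Table 5 read literally.**

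| | Week 12 status in maintenance analysis | Week 56 value |
|---|---|---|
| Later scan exists | missing | later scan (correct) |
| No later scan | missing | the early scan |

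In the second row, section 10.2 excludes LOCF for endoscopy, yet the effect resembles carry-forward. The observed-case sensitivity analysis would not reveal it, because the early scan counts as observed.

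**The case against.** **The maintenance analysis may simply import the induction Week 12 value.** That may be the intention, but no section says so, and the Maintenance SAP has its own Week 12 row. Importing it would also leave Week 56 opening at Rx Day 2. For a subject with no later scan, one scan could then place the subject in the Week 12 responder denominator and also supply the Week 56 outcome. Unless steroid censoring intervened, the subject would automatically count as having maintained response.

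**The Day 1 boundary is the Maintenance SAP's general convention.** This stands. It matches the Maintenance Baseline definition and all four of that SAP's window tables, so the fix must address that definition too.

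**Few subjects can be affected.** This also stands. Re-randomization uses the site's Week 12 reading (Maintenance SAP 5.2), and the first maintenance dose is on or after re-randomization (Induction SAP 9.0), so the scan normally comes first. The primary maintenance population is further limited to Week 12 CR-70 responders (Maintenance SAP 5.1).

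**Stronger readings that the documents do not support.**
- A reader might infer that a missing Week 12 status is coded as failure. The imputation sentence ("According to the NRI imputation approach, all missing values will be considered as" Not Achieved) belongs to a rule for binary efficacy variables. Extending it to an adjustment factor is not supported.
- A reader might infer that subjects who leave early will have no later scan. Protocol 5.3.1.1 lists the discontinuation endoscopy only for discontinuation after Week 26. The same section expects a Week 56/PD endoscopy for all subjects, and footnote d to the Maintenance SAP's study activities table has no Week 26 limit.
- A reader might take the 301 to 307 days as the size of the conflict. They mostly reflect the width of the Week 56 window: a lone scan on Rx Day 9 would still be Week 56, 300 days before nominal.

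**Conclusion.** The conflict stands on the face of the current text and is not just a missing detail: two stated rules give different visits for the same scan over 7 days, maintenance Rx Days 2 to 8, for any first maintenance dose up to induction Rx Day 161.

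The loss of Week 12 status assumes that Maintenance Table 5 selects the Week 12 value. The false Week 56 result requires, in addition, that no later scan exists.

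The effect is minor. It is confined to exploratory, non-ranked maintenance endpoints and probably to few subjects. The documents give no count, and none is estimated here. A reader might infer a threat to the co-primary endoscopic result, but that analysis uses the Induction SAP's window alone and is unaffected. The point is worth correcting because the remedy is cheap and the two reports could otherwise classify one scan differently.

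**What to change.** Three edits to the Maintenance SAP, for SES-CD only:

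1. **Section 6.0, Table 5.** End the Week 12 window at the later of maintenance Rx Day 1 and the end of the Induction SAP's Week 12 window, and start Week 56 the next day. In maintenance days, Week 12 ends at max(1, min(168, D + 7) − D + 1). This gives Rx Day 8, with Week 56 from Rx Day 9, for D ≤ 161. At D = 164 it gives Rx Day 5, with Week 56 from Rx Day 6. The floor at Rx Day 1 matters if maintenance starts after induction Day 168: with D = 170, a scan on induction Day 169 is maintenance Rx Day 0 and stays in Week 12 instead of falling in no window. No scan is counted twice.
2. **Section 10.2.** State that Week 12 endoscopic status, for the CMH/ANCOVA factor and the three conditioned endpoints, comes from this window.
3. **Section 6.0, Maintenance Baseline.** Note that for SES-CD the Week 12 value may fall after Day 1.

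The cost is a small text and table change with some reprogramming, and no new data. The downside is that up to 7 days of maintenance dosing is attributed to Week 12, which the Induction SAP already accepts.
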